### **5.13.2.13. Hepatobiliary Safety**

#### **5.13.2.13.1. Hepatobiliary Disorders**

The AE database will be searched using SMQs to identify events consistent with hepatobiliary disorders. Detailed searching criteria for these AEs can be found in [Appendix 1](#). A summary by treatment and PT within SMQ will be provided. Severe/serious hepatobiliary disorders will be considered AESIs.

#### **5.13.2.13.2. Acute Gallbladder Disease**

The AE database will be searched using pre-defined SMQs to identify events consistent with acute gallbladder diseases. Detailed searching criteria for these AEs can be found in [Appendix 1](#). A summary by treatment and PT within SMQ will be provided. Severe/serious acute gallbladder diseases will be considered AESIs.

#### **5.13.2.13.3. Liver Enzymes**

Analyses for laboratory analyte measurements are described in Section [5.16](#). This section describes additional analyses of liver enzymes. In addition, the following will be provided by treatment groups:

- Shift table of maximum to maximum alanine aminotransferase (ALT) measurement from baseline ( $\leq 1 \times \text{ULN}$ ,  $> 1 \times \text{ULN}$ ) to post-baseline with the following categories:  $\leq 1 \times \text{ULN}$ ,  $> 1$  to  $< 3 \times \text{ULN}$ ,  $\geq 3$  to  $< 5 \times \text{ULN}$ ,  $\geq 5$  to  $< 10 \times \text{ULN}$ ,  $\geq 10 \times \text{ULN}$ .
- Shift table of maximum to maximum aspartate transaminase (AST) measurement from baseline ( $\leq 1 \times \text{ULN}$ ,  $> 1 \times \text{ULN}$ ) to post-baseline with the following categories:  $\leq 1 \times \text{ULN}$ ,  $> 1$  to  $< 3 \times \text{ULN}$ ,  $\geq 3$  to  $< 5 \times \text{ULN}$ ,  $\geq 5$  to  $< 10 \times \text{ULN}$ ,  $\geq 10 \times \text{ULN}$ .
- Shift tables of maximum to maximum total bilirubin and direct bilirubin from baseline to post-baseline with the following categories:  $\leq 1 \times \text{ULN}$ ,  $> 1$  to  $< 2 \times \text{ULN}$ ,  $\geq 2 \times \text{ULN}$ .
- Shift tables of serum alkaline phosphatase (ALP) from baseline to post-baseline with the following categories:  $\leq 1 \times \text{ULN}$ ,  $> 1$  to  $2 \times \text{ULN}$ ,  $\geq 2 \times \text{ULN}$ .

Maximum baseline will be the maximum non-missing observation in the baseline period. The maximum postbaseline value will be the maximum non-missing value from the post baseline period. Planned and unplanned measurements will be included.

### **5.13.2.14. Gastrointestinal Safety**

The time courses of prevalence and incidence (newly-occurring episodes) of nausea, vomiting, diarrhea, and combined will be plotted by treatment and maximum severity.

The maximum severity and duration of treatment-emergent nausea, vomiting, diarrhea, and combined through the end of the study will be summarized by treatment.

The PTs in the gastrointestinal SOC will be used to identify gastrointestinal AEs. The incidence of the resulting TEAEs will be summarized by treatment and PT. Preferred terms with serious/severe cases in the gastrointestinal SOC will be considered as AESIs.

#### **5.13.2.15. Acute Renal Events**

Laboratory measures related to renal safety will be analyzed as specified for laboratory measurements in Section 5.16.

Additionally, two shift tables examining renal function will be created. A min-to-min shift table of estimated glomerular filtration rate (eGFR) estimated by the Chronic Kidney Disease Epidemiology Collaboration (CKD-EPI) equation with units ml/min/1.73m^2, using categories (<30, ≥30 to <45, ≥45 to <60, ≥60 to <90, and ≥90 mL/min/1.73m^2). A max-to-max shift table of urine albumin-to-creatinine ratio (UACR), using the categories UACR<30 mg/g, 30 mg/g ≤ UACR ≤300 mg/g, UACR>300 mg/g (respectively, these represent normal, microalbuminuria, and macroalbuminuria).

The AE database will be searched using SMQs of acute renal failure and chronic kidney disease to identify events consistent with acute renal events. The incidence of the resulting TEAEs will be summarized by treatment and PT. Detailed searching criteria can be found in [Appendix 1](#). Severe/serious acute renal events will be considered as AESI.

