10.3.4.4. Central Laboratory Measures, Vital signs, and Electrocardiograms

Values and change from baseline to postbaseline values of central laboratory measures, vital signs, and selected ECG parameters will be summarized at each scheduled visit. The analysis model to make comparisons among treatment arms relative to continuous change from baseline values assessed over time will be an MMRM, with terms: treatment, visit, and treatment-by-visit interaction, country, baseline SGLT-2i use (Yes or No), and baseline measurement as a covariate. An unstructured covariance structure will model relationship of within-patient errors.

The percentages of patients with treatment-emergent abnormal, high, or low laboratory measures at any time will be summarized and compared between treatment groups by using Fisher's exact test. A treatment-emergent abnormal value is defined as a change from normal value at baseline to an abnormal value at any time during the follow-up. A treatment-emergent high result is defined as a change from a value less than or equal to the high limit at baseline to a value greater than the high limit at any time during Periods II, III, and IV. A treatment-emergent low result is defined as a change from a value greater than or equal to the low limit at baseline to a value less than the low limit at any time during Periods II, III, and IV. High limit and low limit will be provided in SAP.

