There will be 2 estimands of interest in evaluating primary and secondary efficacy objectives. First estimand, the “efficacy” estimand, represents efficacy prior to discontinuation of study drug without confounding effects of rescue therapy for persistent severe hyperglycemia. Analysis relative to “efficacy” estimand will be conducted using EAS. The second estimand, the “treatment-regimen” estimand, represents the efficacy irrespective of adherence to investigational product or introduction of rescue therapy for persistent severe hyperglycemia. Analysis relative to “treatment-regimen” estimand will be conducted using FAS.

Unless specified otherwise, safety analyses will be conducted relative to “treatment-regimen” estimand using the safety analysis set.

End of study participation for a patient will be the earliest of date of death, date of withdrawal from further participation in the study, or date of safety follow-up visit (visit 801). For patients considered to be lost-to-follow-up, end of study participation will be the date of lost-to-follow-up reported by the investigator. Patient data included in database after the last date of study participation (date of death, date of early termination, or date of safety follow-up) will be excluded from statistical analysis. Listing of such data may be provided.

Summary statistics for categorical measures (including categorized continuous measures) will include sample size, frequency, and percentages. Summary statistics for continuous measures will include sample size, mean, standard deviation (SD), median, minimum, and maximum. The summary statistics will be presented by the nominal visit.

Statistical treatment comparisons will only be performed between tirzepatide doses and insulin glargine. Since the trials are not adequately powered to detect differences among tirzepatide doses, comparisons among tirzepatide arms will not be performed unless otherwise specified.

Statistical summaries and results of statistical analysis will be displayed in the following treatment order: 5mg tirzepatide, 10mg tirzepatide, 15mg tirzepatide, and insulin glargine.

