### 5.13. Safety Analysis

Unless specified otherwise, safety assessments will be based on the Safety analysis Set (see [Table GPGM.5.1](#)). All events that occur between the date of first dose of study drug to the date of patient's safety follow-up visit or patient's end of study participation will be included, regardless of the adherence to study drug or initiation of rescue therapy. For assessing benefit and risk profile through 52-weeks, selected safety analyses will be conducted by utilizing safety data from first dose through the date of 52 week visit. Some safety analysis may be conducted after excluding data after the initiation of new antihyperglycemic therapy. Unless specified otherwise, statistical assessment of homogeneity of the distribution of categorical safety responses among treatment arms will be conducted using Fisher's exact test.

Unless specified otherwise, difference among treatment mean change from baseline in continuous safety parameters at all scheduled visits will be assessed via a MMRM using REML. The model will include country/pooled country, baseline HbA1c ( $\leq 8.5\%$ ,  $> 8.5\%$  [ $\leq 69$ ,  $> 69$  mmol/mol]), baseline SGLT2 inhibitor use (Yes or No), treatment group, visit, and treatment-by-visit interaction as fixed effects, and baseline value of the safety parameter as a covariate. To model the covariance structure within patients, the unstructured covariance matrix will be used. If this model fails to converge, the following covariance structures will be tested in order specified in Section 5.12.1.1.

For selected safety parameters, time-to-first-event analysis via Cox proportional hazards model may be conducted. For patients without event, “time-to-event” will be censored as time (in days) from first dose to end of study participation (date of death, study discontinuation, or date of safety follow-up). For patients experiencing the event, “time-to-first-event” will be the time (in days) from first dose to first occurrence of the event.

Where necessary, rate of events will be analyzed using a generalized linear mixed-effects model assuming the number of events follow a negative binomial distribution, treatment as a fixed effect. The logarithm of days during analysis interval will be adjusted as an offset to account for possible unequal treatment duration of follow-up between patients.

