#### **5.13.3. Renal Safety**

A subpopulation of “Patients with T2DM and renal dysfunction” is of study interest, will be identified as  $eGFR < 60 \text{ mL/min/1.73m}^2$  or  $UACR > 300 \text{ mg/g}$  at baseline. The following analyses will be done in this subpopulation:

Summary and change from baseline in  $eGFR$  will be analyzed in MMRM analysis using actual measurements. The same analysis will be done for  $UACR$  in log scale. The analysis will be conducted utilizing for changes from baseline through post-baseline with a MMRM using restricted maximum likelihood (REML). The model will include stratification factors (country/pooled country, baseline  $HbA1c$  ( $\leq 8.5\%$ ,  $> 8.5\%$  [ $\leq 69$ ,  $> 69 \text{ mmol/mol}$ ]), baseline SGLT2 inhibitor use (Yes or No)), treatment group, visit, and treatment-by-visit interaction as fixed effects, and baseline value of the corresponding renal marker (log scale if the corresponding renal parameter is analyzed on the log scale) as a covariate.

Shift table for  $eGFR$  and  $UACR$  will be done in the renal dysfunction subpopulation. Treatment-emergent adverse events in the renal dysfunction subpopulation will be summarized by treatment using MedDRA PT nested within SOC. Serious adverse events in the renal dysfunction subpopulation will be provided. Analyses of changes from minimum baseline value to minimum postbaseline value will be performed for  $eGFR$ . Analyses of changes from maximum baseline value to maximum postbaseline value will be performed for  $UACR$ , Calcitonin, ECG parameters and vitals (pulse, SBP and DBP). Severe hypoglycemia and level 2 hypoglycemia events will be summarized by treatment, excluding hypoglycemia events occurring after initiation of rescue therapy. Post-baseline threshold analysis will be done for  $eGFR$  ( $< 15$ ,  $< 30$ ,  $< 45$ , and  $< 60$ ) and “ $eGFR < 60$  or  $UACR > 300$ ”.

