## 5.16. Clinical Laboratory Evaluation

All laboratory data will be reported in International System of Units and Conventional Units. Out of reference range values will be flagged as high (H) or low (L) in the listings. Descriptive summaries by treatment and by nominal visits will be provided for the baseline and post-baseline values and change from baseline values for selected measurements.

Observed values and change from baseline values for selected measurements for each visit will be displayed graphically for patients who have both a baseline and a postbaseline planned measurement. Unplanned measurements will be excluded from graphs.

A shift table from baseline to postbaseline with unplanned measurements included will be provided for selected measurements. The shift table will include the number and percentage of patients within each baseline category (low, normal, high, or missing) versus each postbaseline category (low, normal, high, or missing) by treatment. Proportion of patients shifted will be compared between treatments using Fisher's exact test.

For qualitative laboratory analytes, the numbers and percentages of patients with normal and abnormal values will be summarized by treatment.

A listing of abnormal findings will be created for laboratory analyte measurements, including qualitative measures. The listing will include patient ID, treatment group, laboratory collection date, study day, analyte name, and analyte finding.

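### Whole-trial UACR is compared only by category shifts, summaries and untransformed change, while the log-scale MMRM is confined to the renal-dysfunction subpopulation

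*SAP*

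**What the plan says.** The protocol's Schedule of Activities has UACR measured in all patients at baseline (Visit 3), at Weeks 42, 52, 78 and 104, and at the final treatment, early termination and follow-up visits.

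For the whole safety analysis set the plan has three layers:

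- **Laboratory section.** SAP 5.13.2.15 begins: "Laboratory measures related to renal safety will be analyzed as specified for laboratory measurements in Section 5.16". Section 5.16 gives by-visit summaries of values and changes for selected measurements, and shift tables for which "Proportion of patients shifted will be compared between treatments using" Fisher's exact test. Under SAP 5.2, "Summary statistics for continuous measures will include sample size, mean, standard deviation (SD), median, minimum, and maximum".
- **UACR shift table.** Section 5.13.2.15 then adds "A max-to-max shift table of urine albumin-to-creatinine ratio (UACR), using the categories" below 30, 30 to 300 and above 300 mg/g.
- **Safety default.** SAP 5.13 lays down a rule for any parameter without its own instruction: "difference among treatment mean change from baseline in continuous safety parameters at all scheduled visits will be assessed via a MMRM using REML". Protocol 10.3.4.4 agrees for central laboratory measures: "The analysis model to make comparisons among treatment arms relative to continuous change from baseline values assessed over time will be an MMRM". Neither mentions a transformation.

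The log-scale model is in SAP 5.13.3. That section defines renal dysfunction as baseline eGFR below 60 or UACR above 300 mg/g and states "The following analyses will be done in this subpopulation". It sets out an MMRM for eGFR and then says "The same analysis will be done for $UACR$ in log scale", with the baseline covariate also logged.

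SAP 5.13.2.3.1 (Pancreatic Enzyme Assessment) specifies an MMRM of the log post-to-baseline ratio for p-amylase and lipase, with no restriction to a subpopulation.

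**The concern.** The SAP chooses the log scale for UACR in one subpopulation and leaves the same analyte untransformed everywhere else, without giving a reason. Three things follow.

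1. **Raw change is dominated by the upper tail.** If treatment multiplies UACR by 0.80, a patient at 20 mg/g changes by 20 × 0.20 = 4 mg/g and a patient at 1000 mg/g by 1000 × 0.20 = 200 mg/g. The second counts fifty times as much, so a few patients set both the mean and its standard error.
2. **The categories hide movement.** A rise from 40 to 250 mg/g stays in one cell. The schedule also gives one baseline UACR against several later values, so a maximum over the later values tends to drift upward in every arm through variability alone.
3. **The two results cannot be set side by side.** A report would show a geometric mean ratio in the subpopulation and a difference in mg/g in all patients.

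Patients with eGFR of 60 or more and UACR of 300 or less, including those with 30 to 300 mg/g and preserved eGFR, get no log-scale comparison. At stake is the precision and interpretability of a safety comparison in a trial where chronic kidney disease is one route of entry.

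**Working it through.** **Step 1. Reproduce the only power figure tied to these arm sizes.** Protocol 10.1 gives 313 per dose, 939 on glargine, HbA1c difference 0.30%, SD 1.3%, 2-sided 0.025 and 90% power.

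- √(1/313 + 1/939) = 0.0653
- z = 0.30 / (1.3 × 0.0653) = 3.54
- power = Φ(3.54 − 2.24) = Φ(1.29) = 0.90, as stated.

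The documents give no UACR mean, SD, effect, power or subpopulation size.

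**Step 2. Assumptions, none from the documents.** UACR lognormal, median 20 mg/g; SD of ln(UACR) σ = 1.3 to 1.6; between-visit correlation ρ = 0.7 to 0.8; true ratio 0.80; 2-sided 0.05; no dropout; subpopulation about 20% of patients. One visit with baseline adjustment stands in for the MMRM. The shift test uses the maximum of three post-baseline visits.

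**Step 3. Log scale, all patients (closed form).** power = Φ( |ln 0.80| / [σ√(1 − ρ²) × 0.0653] − 1.96 ), with |ln 0.80| = 0.223.

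- σ = 1.6, ρ = 0.7: residual SD = 1.6 × √0.51 = 1.143; z = 0.223 / 0.0746 = 2.99; power = Φ(1.03) = 0.85.
- σ = 1.3, ρ = 0.8: residual SD = 1.3 × 0.6 = 0.78; z = 0.223 / 0.0509 = 4.38; power = Φ(2.42) = 0.99.

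**Step 4. Log scale, subpopulation of 20%.** z shrinks by √0.20 = 0.447.

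- 2.99 × 0.447 = 1.34; power = Φ(−0.62) = 0.27.
- 4.38 × 0.447 = 1.96; power = Φ(0.00) = 0.50.

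Simulation gives 28-49%.

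**Step 5. Planned whole-trial comparisons.** These have no simple closed form and were simulated under the same assumptions.

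| Analysis | Power at ratio 0.80 |
|---|---|
| Log scale, all patients | 85-99% |
| Untransformed change, all patients | 22-64% |
| Fisher, any upward max-to-max shift | 50-67% |
| Log scale, subpopulation of about 20% | 28-49% |

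Against the shift test the log scale gains 85 − 50 = 35 points at the lower ends and 99 − 67 = 32 at the upper ends.

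**Step 6. Harm.** |ln 1.25| = |ln 0.80| = 0.223, so steps 3 and 4 are unchanged at ratio 1.25. The simulated shift test has 51-70% power there, so the log scale still leads.

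**Step 7. Other assumptions.** With median 15 or 30 mg/g, σ = 1.4 or 1.7, ρ = 0.6 or 0.8 and ratio 0.80, power is 69-99% for the log scale at Week 52, 13-51% for raw change, 44-64% for the upward-shift test, 40-75% for the three Week 52 categories scored in order, and 19-47% for the log scale in a subpopulation of 13-33%. Relative to the whole-trial log analysis, raw change keeps 14-32% of the information and the subpopulation analysis 14-31%. The ordered Week 52 categories keep 33-63%.

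**The case against.** The case for leaving the plan alone has real substance.

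- **Continuous UACR is already analysed in all patients.** A reader might infer that the shift table is the only whole-trial analysis. The documents do not support that: Section 5.13.2.15 introduces the table as additional to Section 5.16, the summaries include medians, and the MMRM default applies as well. The point is about scale, not absence.
- **Nothing is discarded.** A reader might infer that most of the albuminuria information is lost. The documents give no distribution from which to show this. Under the assumed ones it is true of raw change, but an ordered three-category analysis can lose as little as 37%. The loss is efficiency in the planned comparison; SAP 5.2 permits further analyses even after database lock.
- **The shift table is not powerless.** A reader might infer that a real effect would probably be missed. At ratio 0.80 the upward max-to-max shift test has 50-67% power under the main assumptions, so that does not follow. The table also answers a clinical question about category transitions.
- **UACR is a secondary matter here.** It is not named among the protocol or SAP objectives, has no power claim, and falls under safety assessments without multiplicity control (SAP 5.6). Section 5.13.3 was added as an extra and replaces nothing.

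All of this limits the consequence. None of it explains why UACR is logged in the subpopulation but not in the whole trial, when pancreatic enzymes are logged without restriction. A log analysis added after results are known in an open-label trial would also carry less weight than one specified in advance.

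**Conclusion.** The point holds as an inefficiency and an inconsistency of scale in a safety analysis. For the whole trial, UACR is compared by categories, summaries and untransformed change; the log-scale MMRM is restricted to baseline eGFR below 60 or UACR above 300. Under the main assumptions the whole-trial log analysis gains roughly a third in absolute power over the shift test and more over raw change. The sizes rest entirely on assumed lognormal UACR, and on simplifications of the MMRM and of the number of visits. The ordering is the same under the second set of assumptions and for harm at ratio 1.25. No sample size, error rate, or primary or key secondary conclusion is affected.

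**What to change.** In SAP 5.13.2.15, state that UACR in the whole safety analysis set will be analysed with the log-scale MMRM of Section 5.13.3 in place of the untransformed-change default. The response is the log of the post-to-baseline ratio. Terms are log baseline, the stratification factors, treatment, visit and treatment-by-visit. Report geometric mean ratios versus glargine with confidence intervals at Week 52 and later visits. Keep the three-category shift table as support and the 5.13.3 subpopulation analysis as it is; the two model results are then on the same scale.

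The cost is one SAP sentence and a second run of a model that is already planned, with no new data. Made before database lock it is prespecified; if made later, label it post hoc.

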#### **5.13.2.16. Dehydration**

The AE database will be searched using an SMQ of dehydration to identify events consistent with dehydration. Detailed searching criteria can be found in [Appendix 1](#). Severe/serious dehydration events will be considered AESIs.

#### **5.13.2.17. Metabolic Acidosis, Including Diabetic Ketoacidosis**

Adverse event database will be searched using MedDRA PT terms to identify events consistent with metabolic acidosis. Detailed searching criteria can be found in [Appendix 1](#). Incidence of resulting TEAEs will be summarized by treatment and PT. Severe/serious metabolic acidosis, including diabetic ketoacidosis, will be considered an AESI.

#### **5.13.2.18. Amputation/Peripheral Revascularization**

Adverse event database will be searched using MedDRA PT terms to identify events consistent with amputation or peripheral revascularization. Incidence of resulting TEAEs will be summarized by treatment and PT. Amputation/peripheral revascularization will be considered an AESI.

#### **5.13.2.19. Major Depressive Disorder/Suicidal Ideation**

Adverse event database will be searched using MedDRA PT terms to identify events consistent with major depressive disorder or suicidal ideation. Detailed searching criteria can be found in [Appendix 1](#). Incidence of resulting TEAEs will be summarized by treatment and PT.

Severe/serious major depressive disorder/suicidal ideation or behavior will be considered an AESI.

